8.5 Dissemination of results

Results of the study cannot be disseminated either through reports, presentations at scientific conferences, publications or any other means with out the express written consent of AstraZeneca. AstraZeneca intends to publish the results of the study within 12 months of the end of the study.

9. REPORTING OF ADVERSE EVENTS

The Investigator should report potential adverse drug reactions as post marketing spontaneous reports to authorities/manufacture of suspect drug(s) according to local (US, Canada, France) procedures.


**Health Economics/Outcomes Research Methodological
Protocol Amendment 1: Appendix A**

Drug Substance	Nexium/LDA
Study Code	D961FC00004
Appendix Edition Number	2

**Appendix A
Signatures**

ASTRAZENECA SIGNATURE

A prospective descriptive, multi-national, multi-centre observational study of burden of upper GI-symptoms in subjects with cardiovascular risk or disease receiving treatment with low-dose aspirin

I agree to the terms of this amendment.

**AstraZeneca Research and Development
site representative**

This document contains confidential information, which should not be copied, referred to, released or published without written approval from AstraZeneca. Investigators are cautioned that the information in this protocol may be subject to change and revision.

ICON SIGNATURE

A prospective descriptive, multi-national, multi-centre observational study of burden of upper GI-symptoms in subjects with cardiovascular risk or disease receiving treatment with low-dose aspirin

I agree to the terms of this amendment.

ICON representative

This document contains confidential information, which should not be copied, referred to, released or published without written approval from AstraZeneca. Investigators are cautioned that the information in this protocol may be subject to change and revision.

Clinical Study Protocol Amendment

Amendment Number	1
Drug Substance	Nexium, LDA
Study Code	D961FC00004

A prospective descriptive, multi-national, multi-centre observational study of burden of upper GI-symptoms in subjects with cardiovascular risk or disease receiving treatment with low-dose aspirin

This submission /document contains trade secrets and confidential commercial information, disclosure of which is prohibited without providing advance notice to AstraZeneca and opportunity to object.

Sponsor:

AstraZeneca R&D Molndal
[name]
Sweden

Centres affected by the Amendment:

This amendment affects all centres in the study.

The protocol for the study is to be amended as follows:

The use of the Patient Reported Outcome (PRO) instrument SF-8 will be replaced in all relevant sections of the study protocol with the SF-12 for all scheduled assessments.

Reason for the amendment:

In licensing discussions with the instruments authors, the study team was informed that given recent research the SF-12 would be a more appropriate instrument for assessing the population of interest than the SF-8. No negative consequences for the subjects participating in the study are expected as a result of this change. The change is expected to yield more valid data for the Quality Of Life domain in the study.

Please Note: The described changes in this Amendment affect more than one section in the Clinical Study Protocol (CSP). All sections affected by the change are listed together and ended with “Reason for amendment” and are separated by a dashed line.

Section of protocol affected:

Section 4.2, Table 2.

Previous text:

Table 2 SitePro Survey Domains

Domain	Explanation
Background	Items about gender and LDA use will be entered to facilitate decision on EMA qualification and group.
UGI screening symptoms	Subjects will be asked about UGI symptoms for the past 14 days.
PPI and H2 blocker usage	Evaluates subject use of PPIs and H2 blockers for purposes of EMA qualification, and UGI treatment.
Interaction between UGI and LDA	Evaluates subjects' attribution about UGI symptoms and LDA.
UGI symptoms past 7 days or over past year	Debriefing of UGI symptoms over past 7 days where appropriate, or over past year if no symptoms in past 7 days.
Hospital Anxiety and Depression Scale (HADS)	A subject evaluation on anxiety and depression.
Morisky Medication Taking Behavior Scale	Patients behavior and attributions regarding taking CV medication (modified from original blood pressure medication).
SF-8 Health Survey	A brief general quality of life assessment.
Subjective Symptoms Questionnaire (SSA-P)	Assessment of typical side effects from CV medications, including UGI symptoms.

Revised text:

Table 2 SitePro Survey Domains

Domain	Explanation
Background	Items about gender and LDA use will be entered to facilitate decision on EMA qualification and group.
UGI screening symptoms	Subjects will be asked about UGI symptoms for the past 14 days.
PPI and H2 blocker usage	Evaluates subject use of PPIs and H2 blockers for purposes of EMA qualification, and UGI treatment.

Table 2 **SitePro Survey Domains**

Domain	Explanation
Interaction between UGI and LDA	Evaluates subjects' attribution about UGI symptoms and LDA.
UGI symptoms past 7 days or over past year	Debriefing of UGI symptoms over past 7 days where appropriate, or over past year if no symptoms in past 7 days.
Hospital Anxiety and Depression Scale (HADS)	A subject evaluation on anxiety and depression.
Morisky Medication Taking Behavior Scale	Patients behavior and attributions regarding taking CV medication (modified from original blood pressure medication).
SF-12 Health Survey	A brief general quality of life assessment.
Subjective Symptoms Questionnaire (SSA-P)	Assessment of typical side effects from CV medications, including UGI symptoms.

Section of protocol affected:

Appendix C. Section 1.6 SF-8 Health Survey

Previous text:

SF-8™ Health Survey Scoring Demonstration

This survey asks for your views about your health. This information will help you keep track of how you feel and how well you are able to do your usual activities. Thank you for completing this survey!

Answer every question by selecting the answer as indicated. If you are unsure about how to answer a question, please give the best answer you can.

For each of the following questions, please mark an [x] in the one box that best describes your answer.

1. Overall, how would you rate your health during the **past 4 weeks**?

Excellent Very good Good Fair Poor Very poor

2. During the **past 4 weeks**, how much did physical health problems limit your usual physical activities (such as walking or climbing stairs)?

Not at all Very little Somewhat Quite a lot Could not do physical activities

3. During the **past 4 weeks**, how much difficulty did you have doing your daily work, both at home and away from home, because of your physical health?

None at all A little bit Some Quite a lot Could not do daily work

4. How much bodily pain have you had during the **past 4 weeks**?

None Very mild Mild Moderate Severe Very Severe

5. During the **past 4 weeks**, how much energy did you have?

Very much Quite a lot Some A little None

6. During the **past 4 weeks**, how much did your physical health or emotional problems limit your usual social activities with family or friends?

Not at all Very little Somewhat Quite a lot Could not do social activities

7. During the **past 4 weeks**, how much have you been bothered by **emotional problems** (such as feeling anxious, depressed or irritable)?

Not at all Slightly Moderately Quite a lot Extremely

8. During the **past 4 weeks**, how much did personal or emotional problems keep you from doing your usual work, school or other daily activities?

Not at all

Very little

Somewhat

Quite a lot

**Could not do
daily activities**

Thank you for completing these questions!

Score the survey

Reset the survey form

Revised Text:

Your Health and Well-Being

This survey asks for your views about your health. This information will help keep track of how you feel and how well you are able to do your usual activities. *Thank you for completing this survey!*

For each of the following questions, please mark an in the one box that best describes your answer.

1. In general, would you say your health is:

Excellent	Very good	Good	Fair	Poor
▼	▼	▼	▼	▼
				

2. The following questions are about activities you might do during a typical day. Does your health now limit you in these activities? If so, how much?

Yes, limited a lot	Yes, limited a little	No, not limited at all
▼	▼	▼

- Moderate activities, such as moving a table, pushing a vacuum cleaner, bowling, or playing golf.....
- Climbing several flights of stairs.....

SF-12v2™ Health Survey © 1994, 2002 by QualityMetric Incorporated and Medical Outcomes Trust. All Rights Reserved.
SF-12® a registered trademark of Medical Outcomes Trust.
(SF12v2 Acute, US Version 2.0)

3. During the **past week**, how much of the time have you had any of the following problems with your work or other regular daily activities **as a result of your physical health?**

	All of the time	Most of the time	Some of the time	A little of the time	None of the time
	▼	▼	▼	▼	▼
=Accomplished less than you would like					
=Were limited in the kind of work or other activities.....					

4. During the **past week**, how much of the time have you had any of the following problems with your work or other regular daily activities **as a result of any emotional problems** (such as feeling depressed or anxious)?

	All of the time	Most of the time	Some of the time	A little of the time	None of the time
	▼	▼	▼	▼	▼
=Accomplished less than you would like.....					
=Did work or other activities less carefully than usual					

5. During the **past week**, how much did **pain** interfere with your normal work (including both work outside the home and housework)?

Not at all	A little bit	Moderately	Quite a bit	Extremely
▼	▼	▼	▼	▼
				

SF-12v2™ Health Survey © 1994, 2002 by QualityMetric Incorporated and Medical Outcomes Trust. All Rights Reserved.
 SF-12® a registered trademark of Medical Outcomes Trust.
 (SF12v2 Acute, US Version 2.0)

6. These questions are about how you feel and how things have been with you during the past week. For each question, please give the one answer that comes closest to the way you have been feeling. How much of the time during the past week...

	All of the time	Most of the time	Some of the time	A little of the time	None of the time
Have you felt calm and peaceful?					
Did you have a lot of energy?					
Have you felt downhearted and depressed?					

7. During the past week, how much of the time has your physical health or emotional problems interfered with your social activities (like visiting friends, relatives, etc.)?

All of the time	Most of the time	Some of the time	A little of the time	None of the time
				

Thank you for completing these questions!

SF-12v2™ Health Survey © 1994, 2002 by QualityMetric Incorporated and Medical Outcomes Trust. All Rights Reserved.
 SF-12® a registered trademark of Medical Outcomes Trust.
 (SF12v2 Acute, US Version 2.0)

Reason for Amendment:

In discussions with the instruments authors the study team was informed that the SF-12 would be a more appropriate instrument for assessing the population of interest than the SF-8. No negative consequences for the subjects participating in the study are expected as a result of this change. The change is expected to yield more valid data for the Quality Of Life domain.

Persons who initiated the Amendment:

Clinical Study Team

**Health Economics/Outcomes Research Methodological
Protocol Amendment No 2 Appendix A**

Drug Substance	Nexium/LDA
Study Code	D961FC00004
Edition Number	2
Date	19 June 2008

**Appendix A
Signatures**

ASTRAZENECA SIGNATURE(S)

1. The inclusion and exclusion criteria for taking the survey are being changed such that LDA-naïve patients (patients that do not have a history of taking low-dose aspirin for cardiovascular disease prevention) will no longer qualify.
2. The inclusion and exclusion criteria for taking the survey are being changed such that patients that have been taking low-dose aspirin for cardiovascular disease prevention for up to five years can be enrolled in the survey.
3. The number of subjects planned for enrollment into the EMA Phase is reduced from 420 to approximately 330.

Reason for the amendment:

1. Enrollment of subjects into the EMA (prospective) phase of the study ends on approximately 15 June 2008, or when the required number of subjects have been enrolled. At that time, a sufficient amount of survey (retrospective) data from this

patient population will have been obtained, so the enrollment of additional LDA-naïve patients solely to take the retrospective survey will not be necessary.

2. To promote the enrollment of patients with a history of taking low-dose aspirin for cardiovascular disease prevention, the time frame for use of low-dose aspirin is being extended from 12 months to 5 years.
3. In the original protocol, the goal was to enroll 120 subjects in EMA Group 2 ("Short-term LDA Users": Those having used LDA within a 14-day period of taking the survey). Enrollment for Group 2 has proved to be difficult with about 30 subjects expected to be enrolled into Group 2 before the enrollment for the EMA phase is closed. This reduces the number of expected EMA subjects in all groups from 420 to approximately 330.

Section of protocol affected:

3.1 Design and study flow synopsis

Second Paragraph:

Previous text:

In the first stage of the study, approximately 2,000 subjects who have been prescribed LDA usage in the past 12 months, or those about to begin LDA, will complete a one-time in-office survey using an electronic personal digital assistant (PDA) device (termed SitePro).

Revised text:

In the first stage of the study, approximately 2,000 subjects who have been prescribed LDA usage in the past 5 years will complete a one-time in-office survey using an electronic personal digital assistant (PDA) device (termed SitePro). During the first five months of study enrollment, subjects that are about to commence LDA will also complete the in-office survey.

Fourth Paragraph:

Previous text:

A subset of the subjects of whom all complete the survey will be invited to participate in a three (3) month prospective diary period where real-time assessments will be administered using the ecological momentary assessment (EMA) approach. Four hundred, twenty (420) subjects stratified into three groups varying on length of time using LDA will be asked to use an electronic PRO device (ePRO) to record information about their experience with LDA for the period of 3 months. The ePRO device will prompt (via an audible alarm) the subject three (3) times each day and administer questions regarding the subject's experience with LDA. In

particular, the ePRO device will ask subjects about UGI symptoms, medication use, and about their daily activities and mood. The areas of assessment are listed in Section 4.2.1 (Table 2), and the specific questions are listed in Appendix D. The goal is to obtain EMA data from 350 subjects in the three groups: 200 Naïve LDA users (240 enrolled) who begin LDA use at the time of the study; 100 Short-term LDA users (120 enrolled); and, 50 Long-term LDA users (60 enrolled). A detailed description of the inclusion/exclusion criteria for each EMA group can be found in Section 3.3.3.

Revised text:

A subset of the subjects of whom all complete the survey will be invited to participate in a three (3) month prospective diary period where real-time assessments will be administered using the ecological momentary assessment (EMA) approach. Approximately three hundred, thirty (330) subjects stratified into three groups varying on length of time using LDA will be asked to use an electronic PRO device (ePRO) to record information about their experience with LDA for the period of 3 months. The ePRO device will prompt (via an audible alarm) the subject three (3) times each day and administer questions regarding the subject's experience with LDA. In particular, the ePRO device will ask subjects about UGI symptoms, medication use, and about their daily activities and mood. The areas of assessment are listed in Section 4.2.1 (Table 2), and the specific questions are listed in Appendix D. The goal is to obtain EMA data from 275 subjects in the three groups: 200 Naïve LDA users (240 enrolled) who begin LDA use at the time of the study; 25 Short-term LDA users (approximately 30 enrolled); and, 50 Long-term LDA users (60 enrolled). A detailed description of the inclusion/exclusion criteria for each EMA group can be found in Section 3.3.3.

Section of protocol affected:

3.3.1 Study selection record

Previous text:

Subjects 18 years of age and older, diagnosed as at risk or confirmed with CV disease, and who have been prescribed LDA in the past 12 months or are about to commence LDA will be asked to participate.

Revised text:

Subjects 18 years of age and older, diagnosed as at risk or confirmed with CV disease, and who have been prescribed LDA in the past 5 years will be asked to participate. For the first five months of the study, subjects that are about to commence LDA will also be asked to participate.

Section of protocol affected:

3.3.2.1 inclusion criteria, third bullet point

Previous text:

- Physician prescribed or recommended daily intake of LDA (75-325 mg daily) for cardiovascular disease prevention within the past 12 months, including the day of entry into the study.

Revised text:

- For the first five months of the study: Physician prescribed or recommended daily intake of LDA (75-325 mg daily) for cardiovascular disease prevention within the past 12 months, including the day of entry into the study.
For the remaining months of the study: Physician prescribed or recommended daily intake of LDA (75-325 mg daily) for cardiovascular disease prevention within the past 5 years.

**Health Economics/Outcomes Research Methodological
Protocol: Appendix A**

Drug Substance Nexium, LDA

Study Code D961FC00004

Appendix Edition Number 1

**Appendix A
Signatures**

ASTRAZENECA SIGNATURE

A prospective descriptive, multi-national, multi-centre observational study of burden of upper GI-symptoms in subjects with cardiovascular risk or disease receiving treatment with low-dose aspirin

I agree to the terms of this study protocol.

**AstraZeneca Research and Development
site representative**

This document contains confidential information, which should not be copied, referred to, released or published without written approval from AstraZeneca. Investigators are cautioned that the information in this protocol may be subject to change and revision.

ICON SIGNATURE

A prospective descriptive, multi-national, multi-centre observational study of burden of upper GI-symptoms in subjects with cardiovascular risk or disease receiving treatment with low-dose aspirin

I agree to the terms of this study protocol.

ICON representative

1. SITEPRO CROSS-SECTIONAL SURVEY ITEMS AND QUESTIONNAIRES

Text	Response options
What is your gender?	Female, Male
Please answer the following questions about gastrointestinal symptoms (GI)	
GI symptoms relate to the stomach and intestines, and include indigestion, abdominal pain and/or heartburn.	
Have you experienced any GI symptoms in the past year?	Yes, No
Did you experience the symptoms only during pregnancy?	Yes, No, Not Applicable
Have you experienced any GI symptoms in the past 14 days?	Yes, No
Thinking about your symptoms over the past 14 days, how often did you have the following:	Yes, No
A burning feeling behind your breastbone?	Yes, No
Pain behind your breastbone?	Yes, No
A burning feeling in the center of the upper stomach?	Yes, No
A pain in the center of the upper stomach?	Yes, No
An acid taste in your mouth?	Yes, No
Unpleasant movement of material upwards from the stomach?	Yes, No

Have you taken PPIs or H2 blocker s for acid suppression in the past year?	PPI, H2 blocker, Both, None
Were the PPIs or H2 blockers recommended or prescribed by a physician?	Yes, No
How many months ago did you start?	0-12 months
Please specify the number of weeks ago you started.	0-4 weeks
Have you taken a PPI or H2 blocker for acid suppression in the past 14 days?	PPI, H2 blocker, Both, None
Are you still taking PPIs or H2 blocker s for acid suppression?	PPI, H2 blocker, Both, None
How long ago did you stop taking PPIs or H2 blockers for acid suppression?	0-12 months
Please specify the number of weeks ago you stopped	0-4 weeks
Please answer the following questions about GI symptoms and use of aspirin for CV prevention	
Did you experience any GI symptoms while taking aspirin for CV prevention?	Yes, No
What do you think caused the GI symptoms?	Activity, Food, Drink, Stress, Aspirin, Other, Not Sure
Did you stop taking aspirin for CV prevention because of GI symptoms?	Yes, No
Please answer the following questions for the past 7 days	

How often have you had difficult getting a good night's sleep because of your symptoms?	Daily, Often, Sometimes, Never
< RDQ for past 7 days>	
<XQS for past 7 days>	
<GSRS for past 7 days>	
Please answer the following questions about yourself	
<HADS>	See questionnaire
<SSAP>	See questionnaire
<SF-8>	See questionnaire
<Morisky>	See questionnaire
Thank you!	

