1. INTRODUCTION

1.1 Background

For at least 2 decades low-dose acetylsalicylic acid (LDA) has been used for the prevention of thromboembolic events. The dose range of LDA is 75 to 325 mg daily. The individual doses for different indications vary between countries. The antithrombotic effect of LDA seems to be similar within the dose range of 75 to 325 mg daily (Patrono C et al 2005).

Continuous low-dose ASA treatment is accompanied by a variety of undesirable AEs. These include upper gastrointestinal (GI) symptoms such as dyspeptic symptoms, abdominal pain and/or heartburn (Silagy CA et al 1993, Laheij RFJ et al 2003), peptic ulcers which might be followed by serious ulcer complications such as bleeding, gastric or duodenal perforation and obstruction (Lanas A et al 2006, Yeomans ND et al 2005, García Rodríguez LA and Hernández-Díaz S 2004, CAPRIE Steering Committee 1996, Weil J et al 1995). Even taking ASA in doses as low as 75 mg daily significantly increases the risk of having symptomatic peptic ulcer as well as the risk of having upper GI bleeding compared with not taking aspirin (García Rodríguez LA and Hernández-Díaz S 2004, Weil J et al 1995, Laine L 2006).

While the risk, nature, and development of ulcer and ulcer complications associated with LDA treatment is well documented, less is known about upper GI symptoms. The nature, occurrence rate, and impact of upper GI symptoms associated with LDA treatment, as well as these symptoms' potential influence on compliance with LDA treatment, use of acid inhibitory drugs and other medications is the focus of the current study.

To understand how symptoms develop and are experienced, it is best to ask the subjects themselves (i.e. a patient reported outcome, PRO). Further it is important to understand these symptoms in a non-interventional, naturalistic environment. As such any methodology used needs to be aimed at observing, rather than influencing, the symptoms of interest. Historically, cross-sectional PRO surveys and face-to-face interviews have been used to evaluate subjects symptoms and disease experience. While useful for understanding the subjects' global perspective on their condition, retrospective recall is known to be problematic for documentation of the subjects' day-to-day experience.

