4.2.1 Cross-sectional survey (stage 1)

The following areas or domains will be assessed in the cross-sectional survey. The table below contains sample items or the name of an existing questionnaire. The full listing items for the survey, including all questionnaire items are shown in Appendix C.

Table 2 SitePro Survey Domains

Domain	Explanation
Background	Items about gender and LDA use will be entered to facilitate decision on EMA qualification and group.
UGI screening symptoms	Subjects will be asked about UGI symptoms for the past 14 days.
PPI and H2 blocker usage	Evaluates subject use of PPIs and H2 blockers for purposes of EMA qualification, and UGI treatment.
Interaction between UGI and LDA	Evaluates subjects' attribution about UGI symptoms and LDA.
UGI symptoms past 7 days or over past year	Debriefing of UGI symptoms over past 7 days where appropriate, or over past year if no symptoms in past 7 days.
Hospital Anxiety and Depression Scale (HADS)	A subject evaluation on anxiety and depression.
Morisky Medication Taking Behavior Scale	Patients behavior and attributions regarding taking CV medication (modified from original blood pressure medication).
SF-8 Health Survey	A brief general quality of life assessment.
Subjective Symptoms Questionnaire (SSA-P)	Assessment of typical side effects from CV medications, including UGI symptoms.

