6.2.1 Cross-sectional survey data

Analysis of the data from the survey will primarily be descriptive statistics (e.g., measures of central tendency, correlation matrices) of the demographic characteristics of the sample, frequency of upper GI symptoms, and the nature of those symptoms. In addition, medication usage (amount, type duration of use etc.) will be assessed in relation to demographic, PRO instrument and upper GI related variables.

6.2.2 ePRO-Diary/EMA data

Data for the EMA subjects sub-sample will be examined following analytic techniques typically used in natural history studies (Stone & Shiffman 2007, Shiffman et al 1997). In such studies the same number of observations per subject is not expected. Rather, in natural history studies trends are analyzed utilizing General Estimating Equations (GEE; Zeger SL et al 1988), which allow for varying numbers of observations and take into account the clustering of data within subjects; allowing for the most appropriate autocorrelation structure for this type of data. The variables that will be entered into the GEE models will vary depending upon the specific study objective under evaluation. In general, there will be a focus on those variables related to the onset of upper GI symptoms, and those associated with change in LDA usage.

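### The survey item on when PPI or H2-blocker use began stops at 12 months, so long-standing users cannot answer it truthfully and their duration of use is cut off at one year

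*Protocol*

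**What the plan says.** Appendix C, section 1, opens the acid-suppressant block with the question "Have you taken PPIs or H2 blocker s for acid suppression in the past year". It then asks about physician recommendation and "How many months ago did you start", with a response range of 0 to 12 months and a weeks field of 0 to 4. No response is offered for an earlier start. A later item asks how long ago use stopped, also 0 to 12 months.

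Section 6.2.1 says that "medication usage (amount, type duration of use etc.) will be assessed in relation to demographic, PRO instrument and upper GI related variables". Section 1.1 lists the influence of GI symptoms on the use of acid-inhibitory drugs among the matters the study is about.

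The original survey criterion, kept for the first five months, is LDA prescribed or recommended "for cardiovascular disease prevention within the past 12 months, including the day of entry into the study". Amendment 2 replaces it for the remaining months with "Physician prescribed or recommended daily intake of LDA (75-325 mg daily) for cardiovascular disease prevention within the past 5 years" and explains that "the time frame for use of low-dose aspirin is being extended from 12 months to 5 years". The sections that Amendment 2 shows as revised are 3.1, 3.3.1 and 3.3.2.1. No change to the acid-suppressant items is shown.

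**The concern.** The gate question and the start item do not fit together. The gate admits anyone with use in the past year, including someone who has taken a PPI without a break for several years. The start item then assumes that use began in that same year. The stop item has the same range, and there it is correct: a past-year user who has stopped must have stopped within 12 months. That reasoning does not carry over to the start.

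At stake is the duration of acid-suppressant use, which section 6.2.1 plans to relate to upper GI variables. The cap merges a one-year user with a ten-year user, and any association with duration is flattened among the long-standing users.

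Amendment 2 adds a second, conditional problem. While LDA use was limited to 12 months, the two windows matched. With LDA allowed back to five years and the item unchanged, the survey value can no longer show an acid suppressant that came before LDA in subjects whose LDA began more than 12 months ago.

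**Working it through.** The protocol gives no figure to reproduce; section 6.1 states that no formal sample size calculation was made. The check is whether the response ranges can hold the true answers.

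**Inputs.** Start item: 0 to 12 months (Appendix C, section 1). LDA window: 12 months, then 60 months (section 3.3.2.1 as amended). I read the original criterion as LDA begun within 12 months, as Amendment 2's stated reason does.

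**Step 1: duration.** Let P be the true months since the acid suppressant was started. The largest recordable value is min(P, 12).
- Continuing user, P = 36: recorded 12, true 36.
- User who started 36 months ago and stopped 6 months ago: true duration 36 − 6 = 30 months; recorded 12 − 6 = 6 months.

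This affects every user with P > 12, under either LDA criterion.

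**Step 2: order against LDA.** Let L be months since LDA began, and take cases where the acid suppressant came first (P > L). The recorded order is reversed if min(P, 12) < L.
- L ≤ 12: since P > L, min(P, 12) ≥ L. No reversal is possible; at worst there is a tie at L = 12.
- L ≥ 13: min(P, 12) = 12 < L. Every case is reversed.

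Example: LDA begun 36 months ago, PPI 48 months ago. The PPI start is recorded as 12 at most, so it appears 36 − 12 = 24 months after LDA instead of 48 − 36 = 12 months before it.

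Counting whole-month pairs with P > L and P up to 60:

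| LDA window | Pairs | Reversed | Tied |
|---|---|---|---|
| 12 months | 642 | 0 | 48 |
| 60 months | 1,770 | 1,128 (64%) | 48 |

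With P up to 120 months, the 12-month window gives 0 reversals in 1,362 pairs and the 60-month window gives 4,008 in 5,370 (75%). These are counts over an equal-weight grid. They show where reversal is possible and do not estimate a share of patients.

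**Step 3: illustration under assumptions.** The protocol gives no distribution of acid-suppressant duration. If it were exponential with mean m years, the share of users with a start beyond the range would be e^(−1/m): 61%, 72% and 82% for m = 2, 3 and 5. If LDA duration were also uniform over 0 to 5 years and independent of it, the share reversed would be m(e^(−1/m) − e^(−5/m))/5: 21%, 32% and 45%. The second set applies only to subjects enrolled under the five-year criterion.

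**The case against.** **No ordering analysis is planned.** Section 6.2.1 relates duration to other variables; it does not place acid-suppressant start against LDA start. Appendix C prints no LDA start item either, although Table 2 says that "Items about gender and LDA use will be entered to facilitate decision on EMA qualification and group". This stands, and it limits the order error to a conditional statement. A reader might infer that the study will overstate acid suppression prompted by LDA, by 21 to 45 percentage points. The documents do not support that. It needs an analysis the protocol does not state and durations that are assumed. Subjects from the first five months would also dilute the figures: if they were half of all users, reversals would fall to about 10%, 16% and 23%.

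**The CRF is a second source.** Concomitant medication and GI history are taken on a paper CRF at Visit 1 and reconciled against source records. The protocol does not say whether start dates are recorded, and the CRF fields are not shown. This may reduce the harm but does not repair the item.

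**The cap fits a study with 12 retrospective months.** In part. A 12-month frame can justify not asking how much earlier use began, but the item asks when use started and has no category for a start before the frame.

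**Analysis can handle the cap.** If long-standing users enter 12, it can be read as 12 or more, and the statistical analysis plan, which is not shown, may say so. That supports the remedy for data already collected. It does not make the response range right.

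**The printed appendix may not be the version in use.** It still lists the SF-8, which Amendment 1 replaced, and some text near Amendment 2 and Appendix C is not available. A later correction cannot be excluded; none is visible.

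**Conclusion.** The point holds as an error in a response range. Every past-year PPI or H2-blocker user who started more than 12 months ago lacks a true answer, and the recorded start is capped at one year in a variable that section 6.2.1 marks for analysis.

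The order error is narrower. It arises only for survey subjects enrolled under the five-year criterion whose LDA began more than 12 months ago, and only if order is derived from this item. Within that group it is certain for anyone who took the acid suppressant first, and it always makes the acid suppressant look later than LDA. It cannot arise in the EMA groups, whose LDA use by definition is 12 months or less, or in subjects enrolled under the 12-month criterion. Both of those can still have their duration cut off.

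The number affected cannot be computed from the documents. The study is descriptive and no treatment decision depends on the item, so this is a correction worth making while survey enrolment continues, not a threat to the study as a whole.

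**What to change.** **Item.** Add a response for a start more than 12 months ago, ideally followed by a years field running to 5 and beyond. A range that covers the LDA window leaves only ties at its upper limit and no reversals.

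**Surveys already taken.**
- Treat a recorded 12 as right-censored, meaning 12 months or more. This assumes that long-standing users chose the top value.
- For users who had stopped, duration is then at least 12 minus the months since stopping.
- Use the CRF concomitant medication start date where one is recorded.
- Do not derive the order of acid suppressant and LDA from the capped survey value.

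**Optional.** Ask for the start separately for each class when the subject reports both, and ask directly whether use began before or after aspirin.

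**Cost.** A small SitePro reprogramming change, one analysis rule, and a response format that differs between early and late surveys. The last can be handled by collapsing late responses above 12 months to 12 or more whenever the two periods are pooled.
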